### **14.5 Planned efficacy analyses**

Efficacy variables will be summarized based on the FAS. The summaries described in this section will provide data on maintenance of effect of open-label bimekizumab over 48 weeks. Additionally, it will allow an assessment of the impact of dose adjustments on efficacy results.

Responder efficacy variables (PASI50, PASI75, PASI90, PASI100, IGA score of 0 or 1, and HADS normal scores) will be summarized descriptively using counts and percentages by scheduled visit and PS0016 randomized treatment group and overall. The PASI responder variables are derived relative to the PS0016 Baseline. Missing data will be handled by using nonresponder imputation (NRI), meaning that subjects that discontinue early or who have missing data at a given time point are imputed as though they did not achieve the given response. Supportive summaries will be based on observed case data.

Continuous efficacy variables based on the change from Baseline (PASI, BSA, and HADS) will be summarized using descriptive statistics by scheduled visit and PS0016 randomized treatment group and overall. The table presentations will display descriptive statistics for the PS0016 Baseline and the observed and change from PS0016 Baseline results by scheduled visit for PS0018. Figures for selected variables will also be generated in order to demonstrate the kinetics of response over time. Missing data will be handled by using multiple imputation (MI) via the

Markov-Chain Monte Carlo (MCMC) method. Supportive summaries will be based on observed case data.

In addition to the summaries described above, the impact of dose adjustment on efficacy will be considered. This will be done primarily by summarizing efficacy variables by the 3 adjuster groups as defined in [Section 14.2.2](#). Furthermore, a supportive analysis specifically for single adjusters will be performed in which PASI score will be summarized by visit, where Baseline is recalibrated for each individual subject and defined as the visit where the bimekizumab 320mg Q4W dose is initiated. The visits summarized will be in weeks relative to when the 320mg Q4W dose was started as opposed to the scheduled week of the PS0018 assessment. These summaries will be based on observed data only.

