### **3.6 Treatment assignment and treatment groups**

Treatment assignment for the SS and PK-PPS will be according to the actual treatment received in PS0018, unless stated otherwise in [Table 3–1](#). Analyses of efficacy data (based on the FAS) will be conducted according to the PS0016 randomized treatment group.

Subjects receiving the incorrect treatment (for example due to a dosing error) at a particular visit will be excluded from the PK-PPS as this would be considered as an important protocol deviation. Subjects may be excluded from the analysis at a particular visit (or visits) only, following discussion at the DEM.

Listings will be presented by subjects as randomized in PS0016. Summaries will be presented by treatment group and overall where applicable. See [Table 3–1](#) for the treatment assignment of the 3 different sets of treatment groups.

---

In the TFLs the treatment groups based on the PS0016 randomized treatment group will be displayed as follows, where BKZ refers to bimekizumab and PBO refers to placebo:

- BKZ 320mg + PBO
- BKZ 320mg
- All Subjects

In the TFLs the treatment groups based on the actual PS0018 treatment received (ie PS0018 dose at onset of event or measurement) will be displayed as follows:

- BKZ 160mg Q4W
- BKZ 320mg Q4W
- All BKZ

Lastly there will be the grouping based on dose adjustment in PS0018 defined as follows:

- Nonadjusters – This group consists of subjects who do not experience a dose adjustment during the study.
- Single adjusters – This group consists of subjects who experience just one dose adjustment during the study. Per the protocol, if just a single adjustment occurs, then that adjustment must go from bimekizumab 160mg Q4W to 320mg Q4W.
- Multiple adjusters – This group consists of subjects who experience more than 1 dose adjustment during the study. This means that the subjects in this group dose adjust from bimekizumab 160mg Q4W to 320mg Q4W and then adjust back to 160mg Q4W (with further dose adjustments possible).

For summary purposes, the single and multiple adjuster groupings will be combined.

The treatment group labels and tabulation requirements for each data type are displayed in [Table 3–1](#) **Error! Reference source not found.**

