### **3.9 Changes to protocol-defined analyses**

Change from Baseline in physical examination is listed as a secondary safety variable, in [Section 2.2.1.2](#). Only whether the physical examination was performed and the date it was performed is recorded on the CRF. Thus no summaries for the change from Baseline in physical examination will be provided.”

For the continuous efficacy variables based on the change from Baseline (PASI, BSA, and HADS), imputation for missing values in the protocol is based on multiple imputation (MI) via the Markov Chain Monte Carlo (MCMC) method. However, due to the smaller sample size in PS0018 this may cause problems in the algorithm. For this reason and for consistency with the PS0016 SAP, imputation in PS0018 will instead be based on last observation carried forward (LOCF).

For the dose adjustment groupings, the single and multiple dose adjuster groupings will be combined for summary purposes, unless stated otherwise.

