Furthermore, a supportive analysis specifically for adjusters will be performed in which PASI score will be summarized by visit, where Baseline is recalibrated for each individual subject and defined as the visit where the bimekizumab 320mg Q4W dose is initiated. The visits summarized

will be in weeks relative to when the bimekizumab 320mg Q4W dose was started as opposed to the scheduled week of the PS0018 assessment. These summaries will be based on observed data only.

The PASI50, PASI75, PASI90, and PASI100 responses are based on at least 50%, 75%, 90%, and 100% improvement from Baseline in the PASI score. Thus, the following will apply:

- If the percentage improvement is  $\geq 50\%$  then the subject is a PASI50 responder
- If the percentage improvement is  $\geq 75\%$  then the subject is a PASI75 responder (and is a PASI50 responder also)
- If the percentage improvement is  $\geq 90\%$  then the subject is a PASI90 responder (and is a PASI50 and PASI75 responder also)
- If the percentage improvement is 100% then the subject is a PASI100 responder (and is a PASI50, PASI75 and PASI90 responder also)

The number and percentage of subjects achieving a PASI50, PASI75, PASI90, and PASI100 response will be tabulated by visit and overall and by PS0016 randomized treatment group and by Dose adjustment. The 95% CI for the percentage of responders will be calculated using a Wilson approximation and be included in the tabulation.

In addition, the percentage of responders (including 95% CI) will be plotted at each PS0018 visit for each response variable. Separate plots will be presented for each of PASI50, PASI75, PASI90 and PASI100 with both treatment groups overlaid on the same plot. These plots will be presented by PS0016 randomized treatment and by Dose adjustment separately.

For the purpose of the tabulation the lower and upper 95% confidence limits for the percentage of responders will be truncated at 0 and 100% respectively.

Missing data will be imputed using NRI as described in [Section 4.2.1.1](#). Subjects with missing data will be regarded as non-responders for the PASI50, PASI75, PASI90, and PASI100 variables.

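### SAP 8.2.1 extends the re-baselined PASI summary from single adjusters to all adjusters, so visits after a return to 160mg are pooled on the time-since-320mg-start axis

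*SAP*

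**What the plan says.** Protocol 14.5 plans, for subjects whose dose is raised, "a supportive analysis specifically for single adjusters will be performed in which PASI score will be summarized by visit". Baseline is reset for each subject and visits are counted in weeks from the first 320mg dose. SAP 8.2.1 repeats this with a wider population: "a supportive analysis specifically for adjusters will be performed". It states the reset Baseline as "defined as the visit where the bimekizumab 320mg Q4W dose is initiated" and uses observed data only.

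SAP 3.6 defines the groups. For single adjusters, "if just a single adjustment occurs, then that adjustment must go from bimekizumab 160mg Q4W to 320mg Q4W", so they never go back. Multiple adjusters move from "bimekizumab 160mg Q4W to 320mg Q4W and then adjust back to 160mg Q4W (with further dose adjustments possible". The treatment-group table in SAP 3.6 has only a non-adjuster and an adjuster column. SAP 3.9, which lists changes to the protocol's analyses, says that "the single and multiple dose adjuster groupings will be combined for summary purposes, unless stated otherwise". It does not mention the re-baselined PASI summary.

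**The concern.** In the protocol's version, every treatment-period visit after the reset Baseline belongs to a subject still assigned to 320mg, so time since the start of 320mg is also time on it. Once multiple adjusters are included, that no longer holds. A return to 160mg is allowed when disease is adequately controlled, so the mixing of doses is related to outcome. Its direction cannot be predicted: if control holds at 160mg, the later visits are credited to the 320mg start; if disease worsens again, they count against it.

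This is the only planned PASI summary timed from the dose increase, and Protocol 14.5 presents its efficacy summaries as a way to assess the impact of dose adjustment. A reader of the table could take the late relative weeks as response on continued 320mg when some of those subjects had been back on 160mg for months.

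**Working it through.** There is no planned figure to reproduce. The check compares the texts and then counts visits.

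**Texts side by side**

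| Feature | Protocol 14.5 | SAP 8.2.1 |
|---|---|---|
| Population | Single adjusters | Adjusters (single plus multiple, by SAP 3.6 and 3.9) |
| Time axis | Weeks since 320mg was started | The same |
| Return to 160mg within the population | Excluded by definition | Possible |
| Cut-off or split at return | Not needed | None |
| Which 320mg start is Baseline | Only one exists | Not explicit if there are several |

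Restricting to observed data does not help, because a visit after a return is an observed visit.

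**Visit grid.** Inputs:
- Dosing visits are Weeks 0 to 44 every 4 weeks, 12 in all (SAP 7).
- PASI is assessed before dosing every 4 weeks, and at Week 48 (Protocol Table 5-1 and section 8). The Safety Follow-Up visit is left out of the counts.
- 320mg can start at Week 12 or later (SAP 2.3).
- Return is assumed possible at any later dosing visit.

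Let S be the week 320mg starts and R the week 160mg resumes. Because PASI is taken before dosing, the assessment at R still reflects 320mg and is not counted as after return.

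- PASI visits after the start: (48 − S)/4
- PASI visits after the return: (48 − R)/4
- Share after return: (48 − R)/(48 − S)

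| S | R | Visits after start | Visits after return | Share |
|---|---|---|---|---|
| 12 | 16 | 9 | 8 | 89% |
| 12 | 24 | 9 | 6 | 67% |
| 12 | 36 | 9 | 3 | 33% |
| 12 | 44 | 9 | 1 | 11% |

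Starts from Week 12 to Week 40 leave 8, 7, 6, 5, 4, 3, 2 and 1 later dosing visits for a return, which is 36 pairs of S and R. Every pair puts at least one visit after return on the axis. In the 8 pairs with R = 44 no dosing visit remains, so a second 320mg start is possible by the calendar in 36 − 8 = 28 pairs.

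**From one subject to the whole summary.** The documents do not give the proportion m of adjusters who are multiple adjusters, so it is assumed. If all adjusters start at Week 12 and stay to Week 48, and all multiple adjusters return at Week 24, the share of summarized visits after return is m × 6/9:

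| m | Share of all summarized visits |
|---|---|
| 0 | 0% |
| 10% | 7% |
| 25% | 17% |
| 50% | 33% |

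Under the same assumptions the visits after return all fall in relative weeks 16 to 36, where they make up the full proportion m of the subjects summarized.

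**The case against.** Several points on the other side stand.

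- A reader might infer that the SAP labels these visits as weeks on 320mg. It does not. The axis is weeks since 320mg was started, which stays literally true after a return; the problem is that it can be misread.
- A reader might infer an undeclared departure from the protocol. SAP 3.9 does declare, in general terms, that the adjuster groups are combined. What is missing is any mention of this analysis, where combining changes what the time axis means.
- A reader might infer that the protocol's version isolates the effect of 320mg. It cannot. The study is open-label and uncontrolled, and the increase is offered on a PASI response of at least 50% but below 75%, so some later improvement may be regression to the mean.
- Simply going back to single adjusters is not clean either. It drops, from every relative week, subjects who were later returned to 160mg, often because they responded. Following all adjusters from the first increase is a defensible description of the escalation strategy.
- Dose history is visible elsewhere. Listings flag the 320mg period (SAP 3.1), individual plots show each dose with PASI (SAP 10), and single and multiple adjusters are counted separately (SAP 5.1). With fewer than 3 subjects only n, minimum and maximum are shown (SAP 3.1).
- Protocol 2.2.1 reports a half-life of about 28 days. If kinetics are linear, roughly half the excess exposure remains 4 weeks after the first resumed 160mg dose, so the earliest visits after return are not purely 160mg data.
- The reset Baseline most naturally means the first 320mg start, so that gap needs only a word.

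None of this tells a reader of the summary table which of its visits follow a return.

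**Conclusion.** The point holds in a limited form. SAP 8.2.1 widens the population from single adjusters to all adjusters without naming this analysis in 3.9. Visits after a return to 160mg are therefore pooled on the axis that starts with 320mg, with no cut-off and no separate display. For a subject who starts at Week 12, between 11% and 89% of later treatment-period visits would follow the return. Across the whole summary the share is 7% to 33% if 10% to 50% of adjusters return, on the assumed Week 12 start and Week 24 return. It is nil with no multiple adjusters.

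The documents do not support saying that the efficacy or safety conclusions are compromised. The analysis is supportive and descriptive, the efficacy objective concerns 160mg, and the objective about the dose increase concerns safety and tolerability. No primary result is affected. The matter is worth correcting because the summary is the only one of its kind and the correction is cheap.

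**What to change.** In SAP 8.2.1:
1. Keep all adjusters.
2. Define the recalibrated Baseline as the visit of the first 320mg initiation.
3. In the main version, include visits up to and including the predose assessment at the first resumed 160mg dose, and show later visits separately. Alternatively, add a single-adjuster version as in the protocol.
4. Show at each relative week how many subjects have returned to 160mg.

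In SAP 3.9, name this analysis among the changes and give the reason.

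The cost is a few lines of SAP text, one filter in the program and one extra display. In the example with a Week 12 start and a Week 24 return, the main version keeps 3 later visits (Weeks 16, 20 and 24) and moves 6 to the separate display. The downside is fewer observations at late relative weeks. The cut is also informative, because return follows adequate control: the subjects left at late weeks will tend to be those less well controlled. The count of returned subjects is there so that the reader can see this. No dosing rule changes.

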## 5 STUDY DESIGN

### 5.1 Study description

PS0018 is a multicenter, 48-week, open-label extension study to assess the long-term safety, tolerability, and efficacy of bimekizumab in eligible adult subjects with moderate to severe chronic plaque psoriasis who participated in PS0016.

During the Open-Label Treatment Period, subjects will attend study visits at the site Q4W for study assessments and administration of bimekizumab by study site staff through Week 48. Following completion or early withdrawal from the 48-week Open-Label Treatment Period, subjects will return for a SFU Visit 20 weeks after their last dose of bimekizumab. Subjects withdrawing early from the study will undergo the Early Withdrawal Visit assessments and will enter the SFU Period.

Bimekizumab will initially be administered at a dose of 160mg Q4W subcutaneously (sc) during the 48 week Open Label Treatment Period. There will be an option to increase the dose to 320mg Q4W at the discretion of the Investigator if the subject's PASI response is  $\geq 50\%$  to  $< 75\%$  reduction from the Baseline of PS0016 at Week 12 or later. If the subject's disease is adequately controlled on the 320mg Q4W dose, they may return to 160mg Q4W at the discretion of the Investigator. The decision to return to 160mg Q4W dosing should be based upon treatment response, tolerability, and Investigator discretion, with the aim to use the dosing regimen that achieves the optimal benefit-risk for each subject. If a subject does not achieve a PASI50 at Week 12 or later then they will be withdrawn from the study.

A schedule of study assessments is presented in [Table 5–1](#).

---

A study schematic diagram of PS0018 is presented in [Figure 5–1](#).

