m Bimekizumab will initially be administered at a dose of 160mg Q4W subcutaneously (sc) during the 48 week Open Label Treatment Period. There will be an option to increase the dose to 320mg Q4W at the discretion of the Investigator if the subject’s PASI response is ≥50% to <75% reduction from the Baseline of PS0016 at Week 12 or later. If the subject’s disease is adequately controlled on the 320mg Q4W dose, they may return to 160mg Q4W at the discretion of the Investigator. The decision to return to 160mg Q4W dosing should be based upon treatment response, tolerability, and Investigator discretion, with the aim to use the dosing regimen that achieves the optimal benefit-risk for each subject. If a subject does not achieve a PASI50 at Week 12 or later then they will be withdrawn from the study.

n Subjects should not receive their first dose in PS0018 until at least 4 weeks (+/-3 days) after their last dose in PS0016.

[figure not shown]

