### **7.10 Randomization and numbering of subjects**

This is an open-label extension study and no randomization will be performed. All subjects will receive bimekizumab 160mg Q4W sc with an option to increase the dose to 320mg Q4W at the discretion of the Investigator (see Section 7.2 for further details).

Subjects will continue with the 5-digit subject numbers assigned by the interactive voice or web response system (IXRS) in the preceding study.

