#### **8.4 Week 12 (±3 days)**

The following procedures or assessments will be performed prior to administration of study drug (if applicable):

- Vital signs (blood pressure, pulse rate, and temperature)
- C-SSRS
- TB questionnaire
- PASI
- IGA
- BSA
- HADS
- Obtain blood samples for:
  - Bimekizumab plasma concentration
  - Anti-bimekizumab antibodies
- Obtain urine sample for:
  - Urine pregnancy test for women of childbearing potential
- Concomitant medications
- Record AEs
- Contact the IXRS

- Study medication administration (after all other visit assessments are completed)

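### The re-baselined PASI summary can measure change from the same reading that qualified the subject for 320mg, so it may show improvement even if 320mg adds nothing

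*SAP*

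**What the plan says.** SAP 8.2.1 plans "a supportive analysis specifically for adjusters will be performed in which PASI score will be summarized by visit", in which "Baseline is recalibrated for each individual subject and defined as the visit where the bimekizumab 320mg Q4W dose is initiated". Visits are counted in weeks from the start of 320mg, and "These summaries will be based on observed data only". Protocol 14.5 uses the same definition, but for single adjusters only.

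On the increase itself, Protocol 5.1 says "There will be an option to increase the dose to 320mg Q4W at the discretion of the Investigator". The condition, as worded in the footnote to Protocol Table 5–1, is that the "PASI response is ≥50% to <75% reduction from the Baseline of PS0016 at Week 12 or later". No confirmatory reading is asked for. (Protocol 7.2 words the condition differently, as failing PASI75 at Week 12. Those sections need reconciling, but the point here arises under either wording.)

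Within a dosing visit, PASI comes before the injection. Protocol 8.4, for example, places dosing last: "Study medication administration (after all other visit assessments are completed".

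Subjects with low response leave: "If a subject does not achieve a PASI50 at Week 12 or later then they will be withdrawn from the study". There is no control group: "This is an open-label extension study and no randomization will be performed".

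**The concern.** A subject becomes eligible for 320mg because one PASI reading fell in a middling band. Part of any single reading is visit-to-visit variation. If most subjects respond better than the band, those caught in it at a given visit include some who were temporarily worse than their own usual level, and their next reading is expected to be better whatever dose they receive. Using the qualifying reading as the reference counts that rebound as change after 320mg.

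Two features can add to it. Subjects who then fall below PASI50 are withdrawn, and with observed cases they drop out of later relative weeks. Subjects still improving on 160mg would also show that trend as change after the increase.

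Protocol 14.5 says the efficacy summaries will let the impact of dose adjustment be assessed, and this is the only efficacy summary aligned to the increase. A reader asking whether 320mg helped will look here. What is at stake is how a supportive table is read. The primary safety analysis is not affected.

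**Working it through.** The plan states no figure for this analysis, and its 45 subjects are taken from the feeder study, so there is nothing to reproduce. The check asks what the summary would show if 320mg had no effect.

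**Inputs from the documents:** the band 50% to <75%; eligibility from Week 12; visits every 4 weeks; PASI before dosing; withdrawal below 50%; observed cases.

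**Assumed inputs, not in the documents:** mean percent improvement μ of 60–90; between-subject SD σ_b of 10–15; visit-to-visit SD σ_w of 5–12, independent between visits; PS0016 Baseline PASI of 20 where results are put on the PASI scale. Gains are percentage points of improvement from PS0016 Baseline.

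**1. Closed form, one decision visit.** Let Y = subject level + visit noise, s² = σ_b² + σ_w², ICC = σ_b²/s², a = (50−μ)/s, b = (75−μ)/s.

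- P(selected) = Φ(b) − Φ(a)
- E[Y | selected] = μ + s(φ(a) − φ(b))/P
- Expected gain at the next visit with no effect = (1 − ICC)(μ − E[Y | selected])

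Example, μ = 80, σ_b = 15, σ_w = 10: s = √325 = 18.03; ICC = 225/325 = 0.692; a = −1.664; b = −0.277; P = 0.343; E[Y | selected] = 65.1. Gain = 0.308 × (80 − 65.1) = 4.6 points, or 0.046 × 20 = 0.92 PASI points.

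| Mean improvement | SDs 15, 5 | SDs 15, 10 | SDs 10, 10 |
|---|---|---|---|
| 60 | −0.2 | −0.7 | −1.0 |
| 62.5 | 0.0 | 0.0 | 0.0 |
| 70 | 0.6 | 2.0 | 2.9 |
| 80 | 1.4 | 4.6 | 6.8 |
| 90 | 2.3 | 7.3 | 11.0 |

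The gain is zero when the population mean sits at the middle of the band, (50 + 75)/2 = 62.5, and grows as the mean rises above it.

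**2. Simulation over visits.** Improvement is capped at 100%; 320mg starts at the first visit from Week 12 to Week 44 with 50 ≤ Y < 75; subjects below 50 leave; observed cases; 400,000 subjects per setting. Gain 4 weeks after the increase:

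| Mean improvement | SDs 15, 5 | SDs 15, 10 |
|---|---|---|
| 60 | 0.6 | 1.4 |
| 70 | 1.9 | 4.9 |
| 80 | 3.1 | 8.2 |
| 90 | 4.4 | 11.2 |

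These are larger than in step 1 because repeated looks give each subject more chances to be caught at a low reading. At a mean of 60 without the PASI50 withdrawal, the values become −0.4 and −1.2, so there the apparent gain comes from attrition.

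Over the wider grid (means 80–90, σ_b 10–15, σ_w 5–12) the gain is 1.4 to 12.8 for increases at Week 12 only and 3.1 to 15.5 at the first qualifying visit: about 1.5 to 15.5 in all. At means of 60–65 it is about −1 to +3, with 3.8 at one extreme corner (mean 65, SDs 15 and 12).

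**3. What shrinks or reverses it.**

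- 320mg starts one visit after the qualifying reading: −2.0 to −0.05 at 4 weeks.
- True decline of 2 or 4 points per visit (mean 80, SDs 15 and 5): −2.6 or −8.9 at 12 weeks.
- Visit noise with lag-one correlation 0.5 (mean 80, SDs 12 and 8): 4.1 falls to 2.1 for Week 12 increases, and 7.0 to 3.1 at the first qualifying visit.

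**4. The mean of the decision and preceding visits as reference.** Without drift the residual is 0.7 to 6.4 over the same wider grid. If subjects are still improving (mean 80, SDs 12 and 5, Week 12 increases), 4 points per visit gives 6.0 from the decision visit and 7.0 from the two-visit mean; 6 points per visit gives 8.0 and 10.0.

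**The case against.** A reader might infer more than the documents support, in five ways.

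*That the table will show a false benefit.* No response level or visit variability is given. The gain is near zero or negative when the mean is close to the band, and declining response can hide it. Decline is plausible, since Protocol 5.4 describes 160mg as a test of dose reduction. The largest figures also imply frequent increases: about 58% of subjects at a mean improvement of 90%. This objection stands, and the claim is conditional for that reason.

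*That Baseline is always the qualifying reading.* The increase is optional and may start at a later visit, in which case the artefact largely goes. But nothing discourages starting at the qualifying visit, and PASI is available before that dose.

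*That the earlier course is hidden.* It is not, across the plan as a whole. SAP 10 plans individual plots of PASI with the timing and dose of every administration, SAP 3.1 flags visits on 320mg in the listings, and SAP 8.2 makes the summary against PS0016 Baseline the main look at dose adjustment. What is missing is the pre-increase course in the one summary aligned to the increase.

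*That the reference should be replaced by a two-visit mean.* Step 4 shows that this only partly removes the artefact without drift and enlarges it if subjects are still improving.

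*That a study conclusion is at risk.* The analysis is supportive, descriptive and untested. The stated objective for 320mg is safety and tolerability, and the efficacy objective concerns 160mg. This stands and limits the weight of the point.

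**Conclusion.** The concern holds in conditional form. When 320mg starts at the qualifying visit and mean response lies well above the 50–75% band, the aligned summary is expected to show improvement with no effect of 320mg. At assumed means of 80–90% the gain at the next visit is about 1.5 to 15.5 percentage points; at 60–65% it is about −1 to +3. On the PASI scale, at an assumed Baseline of 20, the 4-week gains in the second table are about 0.1 (0.006 × 20) to 2.2 (0.112 × 20) points.

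The mechanism follows from the documents' own rules. The size rests wholly on assumed means, SDs and independent visit noise. Neither document carries a caveat or a pre-increase display in this summary. The result is a supportive table that cannot by itself separate selection and trend from a dose effect, and a cheap addition would let readers judge.

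**What to change.** In SAP 8.2.1, keep the protocol-defined reference and add:

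1. The same subjects' PASI at all PS0018 visits before the increase, as negative relative weeks in the same table, with a matching mean plot.
2. Paired n at each relative week, because late increases contribute only early weeks and withdrawals thin the later ones.
3. A footnote that change from the initiation visit is subject to regression to the mean and to any ongoing trend, and is not by itself evidence of an effect of 320mg.

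Change from the mean of the initiation and preceding visits may be added, but only as a sensitivity display, for the reason in step 4 of the working.

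The cost is some SAP wording, one larger supportive table and one plot. PASI is already collected every 4 weeks, so no data collection, dose or clinical rule changes. The downside is a busier table and possibly a less favourable-looking result.
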